### Participants

The effect size from previous literature and pilot data (0.25), an alpha=0.05, and power=0.8 was used to derive the total sample size of 135 participants. Assuming 10% attrition, total sample size = 150. Older adults with chronic pain (n=150) recruited from collaborating NGOs will be randomized into 3 different arms: 1) ACT and exercise; 2) art and exercise; and 3) treatment as usual.

Inclusion criteria are:

- age 60 years or above; and
- have depressive symptoms of mild level or above (PHQ > 5)
- have chronic pain (>3 months)
- able to give informed consent to participate

Exclusion Criteria:

- known history of autism, intellectual disability, schizophrenia-spectrum disorder, bipolar disorder, Parkinson's disease, or dementia
- (temporary exclusion criteria) imminent suicidal risk difficulty in communication
- have had stroke, fracture, cardiovascular disease, cardiovascular surgery, artery disease, surgery on vertebrae, and knee replacement in the past 6 months
- physical activity prohibited by a medical professional

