### Assessment Procedures

After basic screening, assessments will be conducted by trained social services staff and trained research assistants employed by the University of Hong Kong for the intervention group.

Assessments will be conducted for all 3 arms at baseline (T0/Intake), completion of intervention (2 months, depending on individual condition) or drop-out (T1/Exit), and follow-up at 3 months (T2/FU) from discharge. Assessment will last for around 60 minutes for all participants.

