## **Data Analysis**

Data will be analysed using a pre-post analysis based on different time points. For the main outcome measures of depressive symptoms/risks, wellbeing, and personal recovery, mixed ANOVA will be used to assess changes from T0/Intake to T1/exit between the two groups. To test for sustained effect after completion of intervention, mixed ANOVA will be used to assess depressive symptoms/risks, wellbeing, pain acceptance, physical ability, and symptoms of pain from T1/Exit to T2/FU within- and between- subjects. All results will be reported with the appropriate effect sizes, along with statistical significance and confidence intervals.

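### The two planned mixed ANOVAs never adjust for the T0 score collected in every arm; adjustment is more efficient in principle, but in this cluster design the gain is unknown and depends on how centre is handled

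*Protocol*

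**What the plan says.** Data Analysis opens with the general approach, "Data will be analysed using a pre-post analysis based on different time points", and then names the method: "mixed ANOVA will be used to assess changes from T0/Intake to T1/exit between the two groups". Sustained effect is assessed by a second mixed ANOVA covering, among other outcomes, "symptoms of pain from T1/Exit to T2/FU within- and between- subjects". No baseline covariate is named for either analysis, and T0 is not a time point in the second.

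The T0 score exists for everyone: "Assessments will be conducted for all 3 arms at baseline (T0/Intake") and at two later visits, according to Assessment Procedures. The first of these is at "completion of intervention (2 months, depending on individual condition) or drop-out (T1/Exit"). The Participants section sizes the trial from "The effect size from previous literature and pilot data (0.25"), with "an alpha=0.05, and power=0.8", to reach 135, and then: "Assuming 10% attrition, total sample size = 150". The Design section describes a cluster randomized trial with 15-20 older adults from each of 10 centres. The protocol gives no T0-T1 correlation, no ICC and no rule for missing visits.

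**The concern.** The protocol fixes the method, so this is a stated choice and not a detail left to a statistical analysis plan. In the T0-T1 analysis, T0 enters only as a repeated outcome. A participant's T1 score is in effect compared after subtracting the whole of T0, whatever the data say about how strongly T0 predicts T1. In the T1-T2 analysis, the group-by-time term concerns only movement after exit, and the between-subjects term averages T1 and T2 with no correction for T0.

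With about 10 centres spread over three arms, baseline differences between arms are likely by chance. A slope fixed at 1 over-corrects for such a difference when the true slope is lower; leaving T0 out does not correct for it. Precision and the handling of imbalance are at stake, using data already planned. A lesser issue is that classical mixed ANOVA needs both visits of a pair, so the two analyses may rest on different participants, and someone seen at T0 and T2 but not at T1 would contribute to neither.

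**Working it through.** **1. The plan's own figures.** 135/(1 - 0.10) = 150 reproduces. The 135 does not follow from the stated inputs alone. Taking 0.25 as Cohen's f (the metric is not named), alpha 0.05 and power 0.80:
- a one-way ANOVA of three groups needs 159;
- with three groups and two time points, the between-groups main effect needs 120 at rho 0.5 and 135 at rho 0.7;
- the group-by-time term needs 42 at rho 0.5 and 27 at rho 0.7.

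The planned rho therefore cannot be recovered from the document, and it is assumed below.

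**2. What the named test is.** With two visits, the group-by-time F equals the one-way F on T1 - T0. In a simulated data set of 3 x 45 participants both were 1.7414.

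**3. Independent participants, equal SDs (variance 1).** Change score: 2(1-rho). Adjusted for T0: 1-rho². Ratio: (1+rho)/2. Saving: (1-rho)/2.

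| rho (assumed) | change | adjusted | ratio | saving |
|---|---|---|---|---|
| 0.3 | 1.40 | 0.91 | 0.65 | 35% |
| 0.5 | 1.00 | 0.75 | 0.75 | 25% |
| 0.7 | 0.60 | 0.51 | 0.85 | 15% |

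Simulated ratios were 0.653, 0.762 and 0.860.

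**4. Clustered participants, individual T0 only.** Take m = 150/10 = 15 per centre, centre effects that do not change between visits, and rho as the correlation within centre. For one centre mean:
- change: 2(1-rho)(1-ICC)/m, because the centre effect cancels;
- adjusted with slope rho: (1-rho)²ICC + (1-rho²)(1-ICC)/m, because part of the centre effect remains.

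The ratio is (1+rho)/2 + m x ICC x (1-rho)/[2(1-ICC)]. At rho 0.3:
- ICC 0.05: 0.65 + 15 x 0.05 x 0.7/1.9 = 0.65 + 0.276 = 0.93;
- ICC 0.10: 0.65 + 15 x 0.10 x 0.7/1.8 = 0.65 + 0.583 = 1.23.

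| ICC (assumed) | rho 0.3 | rho 0.5 | rho 0.7 |
|---|---|---|---|
| 0.05 | 0.93 | 0.95 | 0.97 |
| 0.10 | 1.23 | 1.17 | 1.10 |

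The ratio passes 1 where m x ICC/(1-ICC) = 1, that is at ICC = 1/(m+1): 1/16 = 0.0625 for 15 per centre and 1/21 = 0.048 for 20. If centre effects are only half correlated over time, the saving at ICC 0.05 returns to about 18-30%.

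**5. Centre-mean T0 added.** The relevant correlation is now that of centre means, R = [ICC + rho(1-ICC)/m]/[ICC + (1-ICC)/m], and the ratio with a known slope is (1+R)/2. At rho 0.3:
- ICC 0.05: R = 0.069/0.1133 = 0.61, ratio 0.80;
- ICC 0.10: R = 0.118/0.160 = 0.74, ratio 0.87.

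The slope must be estimated from about 10 - 3 = 7 centre-level degrees of freedom, which multiplies the variance by roughly 1 + 1/(7-2) = 1.2. The ratios become about 0.96 and 1.04. Centre-mean adjustment therefore limits the loss seen in step 4 at ICC 0.10, but with so few centres it does not guarantee a gain.

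**6. Missing visits.** T1 is taken at completion or at drop-out, so a participant who leaves treatment is still meant to have a T0-T1 pair. The need for complete pairs therefore matters mainly for T2.

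**The case against.** The strongest objection is that the trial is cluster randomized. A change score removes a stable centre difference completely, while adjusting for the individual T0 score removes only part of it. Step 4 shows that this can reduce the gain to 3-7% at ICC 0.05 or turn it into a loss at ICC 0.10. This objection stands, and it rules out an unqualified call to add T0 as a covariate.

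Three further points also stand. Change scores are unbiased in expectation under randomization, and mixed ANOVA is a recognised method. Handling of missing visits is commonly left to a statistical analysis plan, and the protocol nowhere says that only complete pairs are used. Equal SDs are also an assumption: entry requires a PHQ score above 5, which may narrow the T0 spread on that scale. If selection halved the T0 variance and left the slope b and the residual variance unchanged, the independent-participant saving would be 0.5(1-b)²/[(1-b²) + 0.5(1-b)²]. That is 0.245/1.155 = 21%, 0.125/0.875 = 14% and 0.045/0.555 = 8% at b = 0.3, 0.5 and 0.7.

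None of this supports the two separate ANOVAs as the better choice. They leave T0 out of the follow-up analysis, and they rely on a slope of exactly 1 in the first without any stated reason.

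**Conclusion.** The point holds as an efficiency weakness and as poor handling of chance baseline imbalance. It is worth correcting, but the validity of the comparison does not depend on it. The algebra is certain; the size is not. It rests on rho, the ICC and the stability of centre effects, none of which the protocol gives. The 15-35% saving applies to independent participants with equal SDs and rho between 0.7 and 0.3. Under clustering with stable centre differences, the gain may be small, absent or reversed.

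A reader might infer more than this, and the documents do not support it:
- **That 15-35% of the variance is lost in this trial, with a matching gain in power or in effective sample size.** Such figures ignore the cluster design and need a correlation that is not stated. That rho 0.7 happens to reproduce 135 for one test does not show it was the planning value.
- **That the planned 10% attrition is discarded.** No complete-pairs rule is written, and T1 is to be taken at drop-out.
- **That the change-score analysis is biased.** With randomized arms it is not, in expectation.

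**What to change.** Replace both mixed ANOVAs with one linear mixed model for each outcome that uses all available visits. It should contain arm at three levels, visit, arm-by-visit, random effects for centre and participant, and small-sample degrees of freedom. Handle baseline at both levels in one of two ways:
- individual T0 and centre-mean T0 as covariates, with T1 and T2 as outcomes; or
- T0 as an outcome with a common baseline mean across arms, and with centre and centre-by-visit effects.

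Report ACT and exercise against art and exercise, and against treatment as usual, at T1 and at T2. Adding T0 as a covariate to the present ANOVA while it remains a repeated outcome would not solve the problem. Before any outcome data are seen, choose between the two forms and state the assumed rho and ICC.

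The change needs no new data and no further participants. It costs a little more analysis work and, if the centre mean is added, one centre-level degree of freedom. With about 10 centres that cost is not negligible (step 5) and should be weighed when choosing the form.

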## **OBJECTIVES**

The objective is to establish evidence of Acceptance and Commitment Therapy (ACT) in combination with exercise in:

Primary Outcomes

- 1) Reducing pain intensity and interference;
- 2) Reducing depression;

Secondary Outcomes

- 3) Reducing anxiety;
- 4) Increasing psychological flexibility;
- 5) Increasing pain-related self-efficacy;
- 6) Increasing quality of life;
- 7) Increasing physical functioning

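### The test of sustained effect runs from exit to follow-up only, so its change terms expect the same null whether the benefit is kept or never existed

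*Protocol*

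**What the plan says.** The Data Analysis section sets out two mixed ANOVAs.

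- **T0 to T1.** For the main outcomes, listed as "depressive symptoms/risks, wellbeing, and personal recovery, mixed ANOVA will be used to assess changes from T0/Intake to T1/exit". This is the only stated analysis that uses T0, and pain is not on its list.
- **T1 to T2.** The purpose is given as "To test for sustained effect after completion of intervention, mixed ANOVA will be used to assess depressive symptoms/risks". The list goes on to wellbeing, pain acceptance and physical ability, and ends with "symptoms of pain from T1/Exit to T2/FU within- and between- subjects".

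The opening sentence of the section, on pre-post analysis at different time points, is general and defines no T0-to-T2 comparison. Under Assessment Procedures the data for one are planned: "Assessments will be conducted for all 3 arms at baseline (T0/Intake", then at exit, then "follow-up at 3 months (T2/FU) from discharge". The Objectives name as a primary outcome "Reducing pain intensity and interference".

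**The concern.** A claim of sustained effect needs an answer to one question: do the arms still differ at follow-up, relative to where they started? An analysis confined to T1 and T2 asks a different one, namely whether the arms moved apart or together after exit. A significant group-by-time term points to loss or late gain, not to maintenance. A non-significant one is expected under full maintenance and equally under no effect at all.

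A claim of durability could therefore rest on a failure to reject, or on a group term that carries the exit effect into the follow-up conclusion. The position is weakest for pain. As written, its only stated analysis is the T1-to-T2 one, so not even an earlier T0-to-T1 result is available to read alongside it.

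**Working it through.** **Algebra, which needs no assumed values.** Let d1 and d2 be the true between-arm differences at T1 and T2, taking the arms to be alike at T0.

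- Group-by-time term: estimates d2 − d1.
- Group term: estimates (d1 + d2)/2.
- Time term: does not compare arms. If there is no common time trend, it too is null both when the benefit is kept and when it never existed.

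| Case | d1 | d2 | Group-by-time | Group |
|---|---|---|---|---|
| Never any effect | 0 | 0 | 0 | 0 |
| Fully kept | δ | δ | 0 | δ |
| Half lost | δ | δ/2 | −δ/2 | 0.75δ |
| All lost by T2 | δ | 0 | −δ | 0.5δ |

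The group-by-time column cannot tell the first two rows apart. The group column can, but it is non-zero in the last row, where nothing is sustained.

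**Illustration of size.** From the protocol: 135 participants before attrition over 3 arms, so 135/3 = 45 per arm, and alpha 0.05. Assumed, because the protocol does not give them: δ = 0.5 SD, outcome SD 1 at each visit, correlation ρ of 0.5, 0.6 or 0.7 between any two visits, independent participants, and two arms compared with a two-sided t test on 88 df. Power comes from the noncentral t with noncentrality difference / (SD × √(2/45)), where the SD is

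- √(2(1 − ρ)) = 1.000 / 0.894 / 0.775 for the T1-to-T2 change;
- √((1 + ρ)/2) = 0.866 / 0.894 / 0.922 for the mean of T1 and T2;
- √(1 − ρ²) = 0.866 / 0.800 / 0.714 for T2 adjusted for T0.

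For example, the group-by-time term at ρ = 0.5 with half the benefit lost has noncentrality 0.25 / (1.000 × √(2/45)) = 1.19 and power 0.216.

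Probability of a significant result at ρ = 0.5 / 0.6 / 0.7:

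| Case | Group-by-time, T1–T2 | Group, mean of T1 and T2 | T2 adjusted for T0 |
|---|---|---|---|
| Never any effect | 0.05 | 0.05 | 0.05 |
| Fully kept | 0.05 | 0.773 / 0.746 / 0.721 | 0.773 / 0.835 / 0.907 |
| Half lost | 0.216 / 0.259 / 0.328 | 0.529 / 0.503 / 0.479 | 0.273 / 0.311 / 0.376 |
| All lost | 0.650 / 0.746 / 0.857 | 0.273 / 0.259 / 0.246 | 0.05 |

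Loss of half the benefit is thus missed by the group-by-time term in 78% / 74% / 67% of trials, and total loss in 35% / 25% / 14%.

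**Reading the two ANOVAs in sequence.** Suppose a significant T0-to-T1 result followed by a non-significant T1-to-T2 change is taken as sustained. In 20,000 simulated trials per setting with the same inputs, among those significant from T0 to T1, the T1-to-T2 change was non-significant in 71% / 68% / 63% when half the benefit was lost and in 24% / 18% / 10% when all of it was lost.

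**Three-arm check.** The mixed ANOVA was also simulated with three arms of 45 (10,000 runs, ρ = 0.5 / 0.7, no clustering). One arm was shifted by 0.25 × 3/√2 = 0.53 SD, which is the protocol's 0.25 read as Cohen's f, a reading the protocol does not confirm.

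- T1-to-T2 group-by-time: rejected in 0.052 / 0.050 with no effect ever and in 0.054 / 0.050 with the benefit fully kept.
- Group term: rejected in 0.295 / 0.272 with the benefit fully lost, and in 0.851 / 0.812 with a 0.53 SD baseline gap and no effect at all.
- T0-to-T2 group-by-time: rejected in 0.050 / 0.051 with no effect, 0.723 / 0.923 when kept, and 0.050 / 0.048 when lost.

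**The case against.** The strongest reply is that the protocol examines within- and between-subject terms together and nowhere says that non-significance will be read as maintenance. It also promises effect sizes and confidence intervals. Suppose the group term must be significant and the group-by-time term must not be. Under the same assumptions that pattern appears in 73% / 71% / 68% of trials when the benefit is kept, in only 9.5% / 6.6% / 3.5% when it is gone, and in 4.75% when it never existed. So the 27% to 25% for the group term alone overstates the ambiguity of the whole model. That stands as a caution on the single-term figures. But the protocol states no such rule, and the rule still leans on non-rejection, does nothing about baseline differences, and shows the same pattern in 41% / 37% / 32% of trials when half the benefit is lost.

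Other points carry some weight:

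- For depressive symptoms and wellbeing, the T0-to-T1 and T1-to-T2 changes add up, with complete data, to the T0-to-T2 change. A point estimate is recoverable; its interval is not.
- Independence flatters every rate, because the design is cluster randomized over 10 centres. With an assumed 3 against 3 centres of 15 and a cluster-level test on 4 df, the T0-adjusted contrast has power of 50–65% at an intracluster correlation of 0.01 and 36–49% at 0.05. The proposed contrast will not reach 77–91% there. Clustering does not change the algebra.
- The absence of pain from the T0-to-T1 list is a defect of its own and would remain after this one is fixed. It matters here only because it removes the sequential reading for pain.
- An SAP may add a T2 contrast. The protocol nevertheless ties sustained effect to the T1-to-T2 window, which is a stated choice and not a detail left open.

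**Conclusion.** The concern holds. That the T1-to-T2 group-by-time term has the same expectation under a kept and a non-existent benefit is exact and needs no assumption about variance, correlation or clustering. The same statement for the time term needs the absence of a common time trend. The group term separates those two cases but mixes exit with follow-up and is open to baseline differences.

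The percentages are illustrative. They rest on an assumed 0.5 SD benefit (0.53 SD in the three-arm check), correlations of 0.5 to 0.7, and independent participants; clustering by centre would change them. This should be corrected before analysis. It is a poor definition of the follow-up question, not a fault in the data to be collected.

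**What to change.** In the Data Analysis section, define the sustained effect as the between-arm difference at T2 adjusted for T0, for BPI severity, BPI interference and PHQ-9, each with a confidence interval. An arm-by-visit model using T0, T1 and T2 would supply it, and it should respect the cluster randomization. Keep the T1-to-T2 change with its interval as a descriptive estimate of how much benefit was lost or gained after exit, and do not call a non-significant change evidence of maintenance.

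The cost is analysis wording only, with no new data or visits.

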### *Intervention*

#### ACT and Exercise:

Participants with chronic pain will participate in an intervention program given twice a week for 8 weeks. ACT designed for chronic pain will be conducted by register Clinical Psychologist, and co-facilitated by registered social workers who are trained by this project and employed by the NGOs. The trained peer supporters will be matched to individual older adults to walk them through the process with regular follow-up. Exercise training program would be designed and instructed by an Exercise Specialist and trained exercise coach.

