## *Physical Assessment*

The purpose of a physical assessment of physical functioning of the elderly prior entering an exercise program is to identify the individuals at risk and effectiveness of the program design.

1. The participant will have their heart rate and blood pressure measured to determine if they are at risk of high blood pressure, of which was one of the leading cause of death and disability in 2010 usually due to unhealthy diet habits, higher percentage of body fat, and physical inactivity (Whelton, P.K. et al, 2018). This can further be supported by the measurements from the Bioelectrical Impedance Analysis (BIA) scale (Kabiri et al, 2015) to determine the individuals body composition.
2. As mentioned previously, risk of falling is closely associated with physical disability and chronic pain. Hence the participant will be assessed on mobility, lower body muscle strength, and balance ability to determine the effectiveness of the intervention:
  - a. Timed Up and Go (TUG) (Podsiadlo and Richardson 1991): a chair with handle is placed 3m away from an obstacle. The individual is instructed to rise from the chair without touching the handles, walk to the point then return to the chair in a seated position as quickly as possible. The rating is based on the number of seconds it takes for the individual to return to initial position where: less than 10 sec. is normal, less than 20 sec. is independent and can displace without aid, and lastly, less than 30 sec. demonstrates that that individual has difficulty walking and requires assistance with daily activity.
  - b. 4-Stage Balance Test “modified” (Phelan et al, 2015): requires the individual to stand in 4 different positions progressively for 10 sec. each. The 4 positions include: stand with feet side-by-side, place the instep of one foot next to the other foot’s big toe, tandem stand, and stand with one foot. If the tandem stand cannot be held for 10 sec. indicates that the elderly is at risk of falling.
  - c. 30 seconds sit to stand test (Rikli, R.E. & Jones, C.J., 2001): the

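### Physical functioning (objective 7) is assigned only to the T1-to-T2 analysis, so no named test measures its change from baseline; pain, a primary outcome, has the same gap

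*Protocol*

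**What the plan says.** The Objectives section lists "Increasing physical functioning" as objective 7, among the secondary outcomes. The Physical Assessment section gives the purpose of the tests: participants are "assessed on mobility, lower body muscle strength, and balance ability to determine the effectiveness of the intervention".

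On timing, the ACT and Exercise section describes an "intervention program given twice a week for 8 weeks", and the art and exercise arm follows the same schedule. Assessment Procedures states: "Assessments will be conducted for all 3 arms at baseline (T0/Intake), completion of intervention (2 months, depending on individual condition) or drop-out (T1/Exit"), followed by T2 at 3 months from discharge. T1 is therefore the end of training.

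The Data Analysis section opens with "Data will be analysed using a pre-post analysis based on different time points". It then assigns outcomes to two windows:

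- T0 to T1: "For the main outcome measures of depressive symptoms/risks, wellbeing, and personal recovery, mixed ANOVA will be used to assess changes from T0/Intake to T1/exit".
- T1 to T2, introduced by "To test for sustained effect after completion of intervention": a mixed ANOVA of depressive symptoms together with "wellbeing, pain acceptance, physical ability, and symptoms of pain from T1/Exit to T2/FU within- and between- subjects".

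Physical ability and symptoms of pain appear in the second list and not in the first.

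**The concern.** An objective worded as an increase needs a comparison that starts before the treatment. The only window named for physical ability starts when the treatment stops. The follow-up analysis is described as a test of whether an effect is sustained. That presupposes an effect shown at T1, and no named test is assigned to show it for physical ability.

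At stake is how objective 7 will be read. If the T1-to-T2 change is taken as its result, a programme that worked and whose benefit lasted looks the same as one that did nothing, and a programme whose benefit partly faded looks worse than usual care. Pain intensity and interference are a primary outcome and sit in the same position, which makes the assignment of outcomes to windows more than a detail.

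**Working it through.** **1. The two lists side by side** (Protocol, Data Analysis)

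| Outcome | T0 to T1 | T1 to T2 |
|---|---|---|
| Depressive symptoms | named | named |
| Wellbeing | named | named |
| Personal recovery | named | not named |
| Pain acceptance | not named | named |
| Physical ability | not named | named |
| Symptoms of pain | not named | named |

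The protocol gives no figure of its own on this point, so there is none to reproduce. What follows illustrates the consequence with assumed values.

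**2. What each contrast measures.** Let the exercise arms gain G by T1 and keep a fraction k of it at T2, with usual care flat. Let b be any difference between the arms at T0. The contrasts, exercise minus usual care, are:

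- change T0 to T1: G
- change T0 to T2: kG
- change T1 to T2 (group by time): (k - 1)G
- average of T1 and T2 (between subjects): b + (1 + k)G/2

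With G = 3 sit-to-stand repetitions (assumed) and b = 0:

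| Kept at T2 | T0-T1 | T0-T2 | T1-T2 change | T1-T2 between subjects |
|---|---|---|---|---|
| 0 of 3 | +3 | 0 | -3 | +1.5 |
| 2 of 3 | +3 | +2 | 2 - 3 = -1 | (3 + 2)/2 = +2.5 |
| 3 of 3 | +3 | +3 | 0 | +3 |
| 4 (further gain) | +3 | +4 | +1 | +3.5 |

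The change term never contains G itself, only what happens to it afterwards. The between-subjects term does contain G, but it also contains b. With G = 0 and b = +2.5, an ineffective programme gives the same +2.5 as the second row. The Design section describes cluster randomisation with 10 centres and three arms, and 10/3 is about 3.3 centres per arm. A chance difference b between arms is a real possibility at that number.

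**3. The same in terms of power.** Assumed: a gain of 0.5 SD in both exercise arms, SD 1, correlation 0.7 between any two visits, clustering ignored. The protocol's 135 participants before attrition give 135/3 = 45 per arm. The test is an F test on 2 and 132 degrees of freedom with noncentrality λ = 45 × Σ(m − m̄)²/v, where the m are the arm means of the change (or sum) and v is its variance. For a change, v = 2(1 − 0.7) = 0.6; for the sum of two visits, v = 2(1 + 0.7) = 3.4.

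| Test | Gain fully kept | Half the gain lost |
|---|---|---|
| T0-T1 group by time | 45 × 0.1667/0.6 = 12.5; about 88% | same |
| T1-T2 group by time | 0; about 5% (its alpha) | 45 × 0.0417/0.6 = 3.1; about 33% |
| T1-T2 between subjects | 45 × 0.6667/3.4 = 8.8; about 76% | 45 × 0.375/3.4 = 5.0; about 49% |

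The percentages are from a simulation of 5,000 runs; the noncentral F gives the same to within a percentage point. In the second column, what the T1-T2 group-by-time test detects is the loss. Accounting for clustering would lower the power of the level comparison further; by how much depends on an intracluster correlation that the protocol does not give.

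**The case against.** The strongest reply is that the planned model is broader than its change term. The protocol says the T1-to-T2 analysis is both within and between subjects, and the between-subjects term compares arms on their post-training level. It has the right sign in every row of the illustration and useful power in the simulation. This stands. A reader might infer that the plan never tests the gain, cannot address objective 7, or will report a benefit as harm. The text does not support any of these: the negative sign belongs to one term under partial loss, and another term of the same model points the other way. What remains is that this term ignores T0 in a trial with few clusters.

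A reader might also infer that a trained arm can only hold or regress after T1. Nothing in the protocol says that participants stop exercising or cannot improve further, as the last row of the first illustration allows.

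A third reply is that the opening pre-post sentence is not restricted by outcome, that the T0-to-T1 sentence is limited to main outcomes, and that the lists are not exhaustive: anxiety and pain self-efficacy are named in neither. Models for secondary outcomes may properly sit in a statistical analysis plan that is not shown here. This carries some weight, and it means one should not assert that the T0 physical data will go unused. But the opening sentence assigns no outcome to any contrast, and for physical ability the protocol is not silent. It names a window, and that window excludes the training period. Nor does the limit to main outcomes explain the absence of pain, which is a primary outcome.

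**Conclusion.** The point holds in this form: the protocol names no baseline-anchored comparison for physical functioning, although objective 7 asks for an increase and the tests are scheduled at T0, T1 and T2. The one named analysis gives a change term that omits the training gain (0 if the gain is kept, -1 in the worked example) and a level term that includes it (+3 and +2.5 respectively) without adjustment for baseline.

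That the window is mismatched rests on the text alone. The sizes rest on assumed gains, retention and correlation, and on ignoring clustering; they show direction and order of magnitude and do not forecast this trial. For physical functioning this is a correction to a secondary objective that should be made before analysis. For pain the same omission touches a primary outcome and deserves the same edit with more urgency.

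**What to change.** In the Data Analysis section, name the Timed Up and Go, 4-stage balance, 30-second sit-to-stand, grip strength and 2-minute step tests in the between-arm T0-to-T1 comparison as the test of objective 7, and add T0 to T2 for persistence. State that the T1-to-T2 change describes what happens after training and will not be read as evidence of an increase. Add pain intensity and interference to the T0-to-T1 analysis as a primary outcome, again with T0 to T2 for persistence. Since the present T0-to-T1 sentence refers to two groups in a three-arm trial, say which arms are compared.

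No visit, test or participant is added. The cost is multiplicity: five physical tests in two windows make 5 × 2 = 10 further omnibus comparisons, before any pairwise contrasts among three arms. At 0.05 each, 10 × 0.05 = 0.5 false positives are expected if nothing works, so they should be reported as secondary, with estimates and confidence intervals.
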